#### **13.4.3.3 Analyses for Secondary Endpoints**

All WOMAC LK3.1 OA Indices, PGA, PGIC, and NRS secondary efficacy endpoints will be analyzed similar to the primary analyses. An MMRM model will be used with change from baseline as the repeated dependent variable, with treatment (HP-5000 and placebo), visit, treatment-by-visit interaction, and the baseline assessment score as covariates.

The observed value and change from baseline each assessment score will also be summarized descriptively by visit using summary statistics in addition to the above noted model.

The proportion of responders and non-responders for WOMAC pain, WOMAC physical function or users of rescue medication will be summarized by visit. Treatment comparisons will be made using a logit model with treatment effect as the only term in the model.

The pain intensity assessed on an 11-point NRS average and worst score between Baseline and each day will be tabulated by day and presented graphically.

A weekly average of all available pain scores will be calculated using the 11-point NRS average and worst score. MMRM model will be used to address the secondary objective to compare for change from baseline between treatment arms by weeks; and data will be presented graphically. The all available scores of daily NRS scores evaluated when the subjects replace the patch and the NRS scores evaluated before any rescue medication use will be analyzed.

The NRS pain score for assessment at Weeks 1, 2, 4, 8, and 12 is a mean of the NRS pain scores reported for pain over the last 24 hours for the 3 days (the last 2 days prior to each clinic visit and the day of the clinical visit) using the 11-point NRS average and worst score. MMRM model will be used to address the secondary objective to compare the change from baseline between treatment arms by weeks; and data will be presented graphically.

To address the objective for rescue medication, the proportion of subjects, the number of days using rescue and total rescue use during the entire treatment period will be summarized by treatment arms.

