7.3 MISSING DATA

The total and subscale scores of any assessment with more than one item, will be derived from individual items. Any individual missing item in any scale will not be imputed. If one or more items are missing at a visit, then the associated total score or subscale score will be set to missing.

Missing WOMAC scores will be imputed and used in sensitivity analyses of the primary and key secondary efficacy as per [section 16.1.4](#) and [16.1.5](#).

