14. STUDY MEDICATION EXPOSURE

Exposure to study medication will be presented for the SAF Set. Investigational product administration for each subject will be summarized in terms of the total number of patches applied by visit, number of patches removed early (due to safety reasons: irritation, discomfort, etc.) by visit, and summary of the reason for early removal.

Each subject’s duration of exposure (days) will also be calculated and summarized by treatment arm.

Derivation:

Duration of exposure (days) = latest of (last patch application date and last patch removal date)
- date of 1st patch application + 1

Refer to [Appendix 4](#) for more details.

A by-subject listing of all drug exposure information collected will be presented.

Noven Pharmaceuticals, Inc.

Protocol HP-5000-US-07

Statistical Analysis Plan

Page 26 of 58

The daily amount of rescue medication used and the daily amount of study drug used will be calculated and presented in a by-subject listing. Deviations from the planned doses (overdose, missed dose, or timing) will be recorded on the eCRF and presented in by-subject listing.

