16.3 OTHER SECONDARY EFFICACY

Other secondary efficacy analyses will be performed for the ITT Set. For each below secondary efficacy variable, tables will be produced that display descriptive and inferential statistics by visit and treatment group. For continuous change from baseline variables descriptive and inferential statistics, comparable to those described in [section 16.1.3](#) for the primary efficacy variable will be presented. With no adjustment for intercurrent events.

For the secondary variables expressed as proportion of subjects with a response that is categorized as binary a logistic regression model will be used to obtain the point estimate of the odds ratio between treatment groups (HP-5000 and placebo) and the associated 95% confidence interval.

16.3.1 WOMAC LK3.1 OA (PAIN) CHANGE FROM BASELINE AT WEEKS 1, 2, 4, AND 8

The change from baseline will be analyzed using a MMRM analysis. As described in [section](#)

Noven Pharmaceuticals, Inc.
Protocol HP-5000-US-07

[16.1.3](#) for the WOMAC pain score, the same MMRM model will be applied.

A plot of the LS Mean change from baseline by visit will be presented.

16.3.2 WOMAC LK3.1 OA (PHYSICAL FUNCTION) CHANGE FROM BASELINE AT WEEKS 1, 2, 4, AND 8

The change from baseline will be analyzed using a MMRM analysis. As described in [section 16.1.3](#) for the WOMAC physical function score, the same MMRM model will be applied.

A plot of the LS Mean change from baseline by visit will be presented.

16.3.3 WOMAC LK3.1 OA (STIFFNESS) CHANGE FROM BASELINE AT WEEKS 1, 2, 4, AND 8

The change from baseline will be analyzed using a MMRM analysis. As described in [section 16.1.3](#) for the WOMAC stiffness score, the same MMRM model will be applied.

A plot of the LS Mean change from baseline by visit will be presented.

16.3.4 WOMAC LK3.1 OA (COMPOSITE SCORE) CHANGE FROM BASELINE AT WEEKS 1, 2, 4, AND 8

The change from baseline will be analyzed using a MMRM analysis. As described in [section 16.1.3](#) for the WOMAC composite score, the same MMRM model will be applied, with no adjustment for intercurrent events. The WOMAC Composite score is calculated by finding the total of the scores for the 3 subscales, WOMAC pain, WOMAC physical function and WOMAC stiffness, and then dividing by 96. Higher scores on the WOMAC indicate worse pain, stiffness, and functional limitations.

16.3.5 CHANGE FROM BASELINE IN PAIN INTENSITY ASSESSED ON AN 11-POINT NRS AT WEEKS 1, 2, 4, 8, AND 12

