16.3.11 TREATMENT RESPONSE: REDUCTION IN THE WOMAC LK3.1 OA INDEX (STIFFNESS)

[figure not shown]
The number and percentage of subjects with reduction in the WOMAC stiffness score of $\geq 30\%$, $\geq 50\%$, $\geq 70\%$, and $\geq 90\%$ at Weeks 1, 2, 4, 8, and 12 (visit 4, 5, 6, 7, and 8) from baseline will be summarized in a table by treatment groups.

The responders are defined as subjects with a reduction in the WOMAC stiffness score of $\geq 30\%$, $\geq 50\%$, $\geq 70\%$, and $\geq 90\%$, and non-responders are defined as subjects with a reduction in the WOMAC stiffness score of $<30\%$, $<50\%$, $<70\%$, and $<90\%$, respectively. Treatment comparisons will be made using a logit model with treatment effect as the only term in the model analyzing the proportion of WOMAC stiffness score responders. For each comparison, an estimate of the odds ratio, corresponding Wald 95% CI, and p-value will be presented.

16.3.12 PROPORTION OF SUBJECTS, THE NUMBER OF DAYS, AND THE TOTAL NUMBER OF RESCUE MEDICATION**TABLETS USED DURING THE TREATMENT PHASE**

Proportion of subjects who used rescue medication at any time during the entire treatment period and descriptive statistics for the number of days these subjects used rescue medication and the total number of rescue medication tablets used during the treatment phase will be presented by treatment arm.

The number and percentage of subjects using rescue medication will be summarized by treatment and overall. A logit model will be used to compare treatment against placebo. This model will not contain any baseline covariates but will present an estimate of the odds ratio, Wald 95% confidence interval, and p-value for use of rescue medication. A by-subject listing of

Noven Pharmaceuticals, Inc.

Protocol HP-5000-US-07

Statistical Analysis Plan

Page 38 of 58

all efficacy assessments collected will be presented.

For number of days of rescue medication and number of tablets of rescue medication during the treatment phase, an independent two sample t-test will be used to compare treatment against placebo. An estimate of the difference, the 95% CI, and the p-value will be presented. If the normality assumption is not supported by the data, a Wilcoxon Rank Sum Test will be used.

16.3.13 THE ONSET OF THE EFFECT: PAIN INTENSITY ASSESSED ON AN 11-POINT NRS CHANGE FROM BASELINE

Onset of the effect of HP-5000 will be defined as the first significant difference in NRS pain reduction between HP-5000 vs Placebo.

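### Rescue days and tablets are compared between arms as raw totals, with no allowance for unequal diary follow-up

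*SAP*

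**What the plan says.** SAP 16.3.12 gives the proportion of rescue users with a logit comparison, then "descriptive statistics for the number of days these subjects used rescue medication" and the total tablets. For days and tablets, "an independent two sample t-test will be used to compare treatment against" placebo, reported as a difference, 95% CI and p-value. The fallback is on the same totals: "If the normality assumption is not supported by the data, a Wilcoxon Rank Sum Test will be used". Protocol 13.4.3.3 also works with totals and names no test: "the number of days using rescue and total rescue use during the entire treatment period will be summarized by treatment arms".

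Nothing elsewhere brings in time on study:

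- The SAP 16.3 preamble sets these analyses on the ITT set. Its phrase "With no adjustment for intercurrent events" follows a sentence about change-from-baseline variables and supplies no rule for rescue totals.
- SAP 7.3 deals with multi-item scales: "Any individual missing item in any scale will not be imputed". It is silent on diary days after a subject leaves.
- SAP 14 derives duration of exposure for the safety exposure summary only. Per-day rescue use goes no further than a listing: "The daily amount of rescue medication used and the daily amount of study drug used will be calculated and presented in a by-subject listing".

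**The concern.** A total count of days or tablets is a daily rate multiplied by the time over which it could be counted. A subject who stops filling in the diary at Week 4 contributes a small total even if rescue was taken on every allowed day. If one arm loses more diary follow-up than the other, a difference in observation time appears as a difference in rescue use and is reported with a confidence interval and p-value. SAP 16.1.5 itself allows for unequal discontinuation between arms and provides sensitivity analyses for the WOMAC endpoints, but nothing comparable for rescue. The pattern of rescue use is a stated secondary objective (Protocol 6.3).

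Two smaller points go with this. The descriptives for days are written for users only, which conditions on a post-randomisation outcome. The SAP also does not say whether diary days after a subject stops the patch but stays in the study belong to the treatment phase.

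**Working it through.** The documents give no rescue rate, SD or dropout rate for this endpoint, and the sample size and effect size are redacted. There is therefore no plan figure to reproduce. Dropout, daily use and n below are assumptions.

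**1. Permitted rescue days.** The nominal visits fall on Days 0, 7, 14, 28, 56 and 84 (Protocol 10.2). Rescue is barred from Baseline through Visit 4 (Days 0–7, 8 days), and on the day of and the 2 days before Visits 5–8 (4 × 3 = 12 days) (Protocol 9.11, SAP 3.1). Days 0–84 are 85 days, and 85 − 8 − 12 = 65. Permitted days accrue as 0 by Day 7, 4 by Day 14, 15 by Day 28, 40 by Day 56 and 65 by Day 84. A Week 4 leaver has 15/65 = 23% of a completer's permitted days. A compliant subject who leaves by Week 1 scores zero.

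**2. Expected permitted days per subject.** With a proportion d lost and P permitted days accrued by leavers, E = (1 − d) × 65 + d × P. For Week 4 leavers:

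- 25% lost: 0.75 × 65 + 0.25 × 15 = 52.5
- 15% lost: 0.85 × 65 + 0.15 × 15 = 57.5
- Ratio: 57.5/52.5 = 1.095

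| When leavers go | P | 25% lost | 15% lost | Ratio |
|---|---|---|---|---|
| Uniform over Days 0–83 | 29.2 | 56.0 | 59.6 | 1.064 |
| Week 4 | 15 | 52.5 | 57.5 | 1.095 |
| By Week 1 | 0 | 48.75 | 55.25 | 1.133 |

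At an assumed 0.3 rescue days per permitted day, the Week 4 row gives 0.3 × 52.5 = 15.75 against 0.3 × 57.5 = 17.25 rescue days with identical behaviour. With equal loss (20% in each arm) both arms have 55.0 permitted days and there is no bias.

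**3. When the direction holds.** If leavers use rescue m times as fast per day as stayers, the mean total is proportional to (1 − d) × 65 + d × m × P. More loss lowers it whenever m × P < 65. The direction reverses only above m = 65/29.2 ≈ 2.2 for uniform leaving, or 65/15 ≈ 4.3 for Week 4 leaving.

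**4. Effect on the tests.** Simulation used 1,500 trials per setting and n per arm of 100, 175, 250 and 400. Daily use was identical in both arms (mean 0.3 per permitted day, beta-distributed between subjects). Rejection rates at two-sided 0.05, as ranges over n:

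| Loss, timing | t-test | Wilcoxon | Rate per permitted day |
|---|---|---|---|
| 20% vs 20%, uniform | 4.9–5.9% | 5.1–6.4% | 5.1–5.7% |
| 10% vs 20%, uniform | 7.9–13.7% | 8.5–14.5% | 4.3–6.0% |
| 15% vs 30%, uniform | 9.7–24.5% | 9.4–26.5% | 4.3–5.7% |
| 15% vs 30%, within 4 weeks | 17.7–54.9% | 25.0–70.2% | 5.3–5.7% |

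The Wilcoxon fallback does not cure the problem. A rate does.

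**5. Observed days as denominator.** Barred days cluster early, so this denominator leaves a small residue. In the Week 4 example, observed days are 0.75 × 85 + 0.25 × 29 = 71.0 and 0.85 × 85 + 0.15 × 29 = 76.6. Permitted days per observed day are 52.5/71.0 = 0.739 and 57.5/76.6 = 0.751, a ratio of 1.015 in place of 1.095.

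**The case against.** The strongest objection is retention. The amended Protocol 8.2.3 says subjects should not be asked to withdraw for adverse events or lack of efficacy, and it encourages those who stop treatment to attend all visits and keep the eDiary to the end of the study. A reader might infer that every treatment discontinuation truncates the rescue count. The documents do not support that: the mechanism needs study withdrawal or a stopped diary. This objection stands and narrows the point. It does not remove it, because subjects can still withdraw, and because the SAP leaves the status of off-treatment diary days undefined.

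The protocol defines the endpoint as days and total tablets over the treatment phase, so dropping the totals would change the endpoint. That also stands, and the totals should still be reported.

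A reader might take the users-only wording to apply to the t-test. It does not: that wording governs the descriptives, and the test sentence has no such limit on an ITT analysis. The descriptives also sit beside the proportion of users, so they can be read as a two-part summary.

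Rescue also covers headache and fever (Protocol 9.11), so the totals are not a pure measure of knee efficacy. That is true but does not affect the bias.

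**Conclusion.** The concern holds in a limited form. The planned comparison has no exposure term. If diary follow-up is lost unequally, and leavers and stayers use rescue at similar daily rates, the arm losing more subjects looks like the lower user. With Week 4 leavers and assumed loss of 25% versus 15%, the gap is about 9.5%. Over the leaving times tabulated it runs from 6.4% to 13.3%, and it is nil when loss is equal. These sizes rest on assumed dropout and on every leaver's diary ending.

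Two stronger readings should be resisted. A reader might infer that the analysis is tilted towards HP-5000. The documents do not show this. In the imbalance SAP 16.1.5 contemplates, with less discontinuation on active, the error under equal daily use would run against HP-5000. A reader might also infer that the trial's main conclusion is at risk. It is not: the rescue endpoints are outside the fixed sequence (SAP 7.4, Protocol 13.4.3.2), so the primary result and the family-wise error rate are untouched.

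**What to change.** - Keep total rescue days and tablets, as the protocol defines them, as descriptives for all ITT subjects with zeros included.
- Base the between-arm comparison on an exposure-adjusted rate, for example a negative binomial model (or quasi-Poisson with robust variance) with treatment as factor and log(days under eDiary observation in the treatment phase) as offset. Report the rate ratio and 95% CI.
- Use observed rather than permitted days in the main model. Permitted days are zero for anyone who leaves by Visit 4, so the log offset is undefined. Rescue taken on barred days would also enter the numerator but not the denominator. Observed days are at least 1 for any subject with diary follow-up.
- Add a per-permitted-day rate as a sensitivity analysis. It removes the residue of about 1.5% shown in the working.
- State whether diary days after stopping the patch, up to Week 12, count as treatment phase.
- Record the change in SAP 3.3, which now reads as not applicable.

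The cost is SAP wording, one extra model and one derived variable from eDiary data already collected. The offset corrects for unequal time under observation. It does not fully correct for informative dropout, and the write-up should say so.

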16.3.16 RESPONDERS AND NON-RESPONDERS ANALYSIS

The proportion of subjects who are responders for WOMAC pain score, WOMAC physical function score, stiffness score, composite score, NRS, and users of rescue medication will be based on $\geq X\%$ improvement from baseline^[6]. At each time point, subjects having $X\%$ or greater improvement from baseline in WOMAC pain score will be defined as “responders”. The percentage change from baseline is defined as $(\text{Value at Week } X - \text{Baseline value}) * 100 / (\text{Baseline value})$. In other words, the responder indicator will be set to 1 if the percentage change is less than or equal to $-X\%$ and set to 0 if the percentage change is greater than $-X\%$ or missing. The different levels of required percent improvement from baseline are $X=5\%$ to 100% with 5% increments. These different thresholds for improvement will be summarized by visit. Results will be reported by means of a graph with response threshold on the X-axis and proportion of subjects who are responders in each treatment group on the Y-axis, this figure will only be completed for the WOMAC pain score. Corresponding statistics will be presented in a summary table. The same statistics will be provided for WOMAC stiffness score, physical function score, and composite score.

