### 8.2.2 Exclusion Criteria

A subject will be excluded from the study if the he or she meets any of the following criteria:

- Body mass index (BMI)  $> 40 \text{ kg/m}^2$  at Screening (Visit 1).
- The non-target knee pain severity score is [REDACTED] at Screening (Visit 1) and Baseline (Day 0).
- Any subject who did not follow the restriction of prohibited therapies during Washout period (including use of rescue medication within 3 calendar days prior to the Baseline Visit).

4. Arthritis of the target knee that is not caused by OA but caused by diseases such as rheumatoid arthritis, gout, psoriasis, syphilitic arthropathy, ochronosis, metabolic or other primary bone disease, or acute traumatic injury.
5. Any subject diagnosed with fibromyalgia.
6. Any other painful or disabling conditions affecting the target knee or leg.
7. Clinically significant elevation of serum creatinine ( $\geq 2$  mg/dL), aspartate aminotransferase (AST) or alanine aminotransferase (ALT) (at  $3 \times$  upper limit of normal [ULN]) at the Screening Visit.
8. Known allergy or hypersensitivity to diclofenac, APAP, acetylsalicylic acid (aspirin [ASA]), or any other NSAID, [REDACTED], glycerin, propylene glycol, or ethanol.
9. Severe uncontrolled cardiovascular, renal, hepatic, or other systemic illness/disease.
10. A documented gastroduodenal ulcer (by upper GI series or endoscopy), GI perforation or any GI bleeding (except hemorrhoidal bleeding) within 6 months prior to Screening Visit.
11. Documented history of alcohol or drug abuse within 1 year prior to study entry or positive alcohol/drug screen findings at Screening or Baseline.
12. Presence of chondrocalcinosis on X-ray if associated with a history of pseudogout or inflammatory flare-ups.
13. MAJOR SURGERY: Previous damage or surgery to the target knee at any time (i.e., damage/reconstruction of the anterior or posterior cruciate ligaments).
14. MINOR SURGERY on the target knee defined as anything other than major surgery (as defined above) within 1 year before study enrollment.
15. Treatment with oral or intra-muscular corticosteroids within 90 days of Screening Visit, treatment of the target knee with topical or intra-articular corticosteroids within 90 days of Screening Visit, or topical or intra-articular corticosteroid treatment of any other joint within 30 days of Screening Visit.

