3.3 CHANGES TO ANALYSIS FROM PROTOCOL

Not Applicable

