6.2 BASELINE AND POST STUDY ASSESSMENT

Baseline is defined as the last non-missing measurement taken on or prior to the first patch application date. In the case where the last non-missing measurement and the reference start date coincide, that measurement will be considered pre-baseline if the assessment is planned per protocol to take place prior to first study medication administration.

Post-study assessment is defined as a non-missing measurement taken on or after the date of the last patch removal. In the case where the dates coincide, time of the measurement should be after the last patch removal time to be considered post study assessment. This will be applied to identify post study medications and adverse events.

Noven Pharmaceuticals, Inc.

Protocol HP-5000-US-07

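### SAP 16.3.16 puts rescue-medication users under a percent-improvement-from-baseline rule that cannot separate the arms when baseline rescue use is zero, so the protocol's by-visit user comparison has no workable definition

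*SAP*

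**What the plan says.** The opening sentence of SAP 16.3.16 lists the WOMAC scores, "composite score, NRS, and users of rescue medication will be based on" at least X% improvement from baseline. The percent change is the visit value minus baseline, divided by baseline. The indicator is 1 at or below minus X%. It is "set to 0 if the percentage change is greater than" minus X%, "or missing. The different levels of required percent improvement from baseline are" 5% to 100% in steps of 5%.

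No baseline specific to rescue use appears in the SAP. The general rule in SAP 6.2 reads: "Baseline is defined as the last non-missing measurement taken on or prior to the first patch application date".

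The protocol (9.11) bars rescue in the days before the Baseline Visit and on the Baseline day. Exclusion 3 in the amended protocol 8.2.2 covers failure to keep to the washout restrictions, "including use of rescue medication within 3 calendar days prior to the Baseline Visit". Earlier in washout, rescue is allowed up to 2 g/day (10.1.1.2).

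Protocol 13.4.3.3 treats rescue differently: the proportion of responders "or users of rescue medication will be summarized by visit", compared with a logit model whose only term is treatment. SAP 3.3, on changes from the protocol, says "Not Applicable".

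**The concern.** A percent change needs a non-zero baseline. For pain, function or stiffness that is reasonable, because subjects enter with symptoms. For rescue use, the design drives the value just before the first patch to zero. A rule that divides by that value, and then counts the undefined result as failure, returns the same answer whether the patch lowers rescue use or raises it.

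The protocol's measure is a yes/no status that needs no baseline. Replacing it with a percent-improvement rule changes the analysis without a record of the change. At stake is one by-visit comparison on a secondary endpoint outside the fixed testing sequence.

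**Working it through.** The plan gives no figure for rescue responders, and sample size and effect size are redacted, so there is nothing to reproduce. The check is whether the rule's output can depend on treatment.

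**Inputs.**
- Rule: percent change = (v − b) × 100 / b; responder = 1 if ≤ −X%, otherwise 0, and 0 if missing (SAP 16.3.16).
- Thresholds: X = 5, 10, …, 100, which is 20 values.
- v: post-baseline tablets per day, 0 to 4 (2 g/day as 4 × 500 mg, protocol 9.11).
- b: baseline tablets per day.

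**Case 1: b = 0** (SAP 6.2 with daily use, compliant eligible subject).
- v = 0 gives 0/0; v = 1 to 4 gives v × 100 / 0. Both are undefined, hence missing, hence coded 0.
- Responder at 0 of 20 thresholds for every v from 0 to 4.
- Extreme contrast: HP-5000 at 0 and placebo at 4 tablets/day gives 0% against 0%. Reversing the arms gives the same. The odds ratio cannot be estimated.

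**Case 2: b > 0** (for instance washout use, which the SAP does not specify; values assumed).

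| b | v | Percent change | Highest X met |
|---|---|---|---|
| 4 | 0 | −100% | 100 |
| 4 | 1 | (1 − 4) × 100 / 4 = −75% | 75 |
| 4 | 2 | −50% | 50 |
| 4 | 3 | −25% | 25 |
| 2 | 0 | −100% | 100 |
| 2 | 1 | −50% | 50 |
| 1 | 0 | −100% | 100 |

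Here the rule can discriminate, with two limits. Subjects with no washout use still have b = 0 and are coded as non-responders: if 30%, 50% or 70% used rescue in washout (assumed), then 70%, 50% or 30% are undefined. Also, the SAP does not say which days supply v. If v is the clinic-day value, the protocol bars rescue on every clinic day from V4 to V8, so a compliant subject has v = 0, and any b > 0 gives (0 − b) × 100 / b = −100%. Every such subject then responds at all 20 thresholds in both arms.

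**What the protocol's measure needs.** Yes/no use requires no baseline, but it does require an interval, because use on the visit day is barred. At nominal visit days (7, 14, 28, 56, 84), and with rescue also barred in the 2 days before V5 to V8, the permitted days are:
- V4–V5: days 8 to 11, 4 days
- V5–V6: days 15 to 25, 11 days
- V6–V7: days 29 to 53, 25 days
- V7–V8: days 57 to 81, 25 days
- V3–V4: none

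Four intervals can therefore carry information and the first cannot.

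**The case against.** There are four arguments on the other side.

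**The rescue objective is served elsewhere.** Protocol 13.4.3.3 ties that objective to users, days and total use over the entire treatment period. SAP 16.3.12 delivers this with a logit for users and a t-test or Wilcoxon test for days and tablets, none of which needs a baseline. This stands in full. A reader might infer that the rescue analysis is lost, and the documents do not support that.

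**By-visit tables may already be implied.** The lead-in to SAP 16.3 promises descriptive and inferential tables by visit for each secondary variable, with logistic regression for binary ones. This stands in part. Section 16.3.12 counts use at any time in the treatment period, and nothing defines who is a user at a visit.

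**No rescue table is clearly planned under the percent rule.** After its opening list, 16.3.16 says that subjects with X% or "greater improvement from baseline in WOMAC pain score will be defined as" responders, and it promises the same statistics only for the other WOMAC scores. The table shells are not available to settle the matter. This stands: the result of 0% against 0% is what the rule gives if applied, not an output the SAP commits to.

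**Zero baseline is an inference.** A reader might infer that everyone in both arms must be a non-responder. That goes too far. A washout-based baseline, or a last recorded tablet count where only days of use are entered, could exceed zero, and the ITT set may include subjects enrolled in error. The inference holds for compliant eligible subjects under SAP 6.2 with daily use.

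**Conclusion.** The concern holds in a limited form. The rule stated in SAP 16.3.16 does not suit rescue use. For compliant eligible subjects under the only baseline rule the SAP gives, it classes all as non-responders at all 20 thresholds in both arms, whatever the treatment effect. It also departs from the yes/no by-visit logit in protocol 13.4.3.3 while SAP 3.3 declares no change.

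This rests on reading baseline use as the daily value at or before the first patch, and on compliance with the pre-Baseline bar. A positive baseline would let the rule discriminate for some subjects, but the SAP specifies neither such a baseline nor the post-baseline days to compare with it.

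The consequence is minor. What lacks a workable definition is the by-visit user comparison. The whole-period rescue analyses, the primary endpoint and the key secondary endpoints are unaffected. The correction is still worth making, because it replaces a stated rule that yields an uninformative result with the protocol's own measure.

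**What to change.** In SAP 16.3.16, delete rescue-medication users from the list governed by the percent-improvement rule.

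In SAP 16.3.12, add that rescue use, defined as at least one tablet recorded in the eDiary, is classified yes/no for each interval between consecutive clinic visits from V4 to V8, summarised by visit, and compared with the planned treatment-only logit. Note that the V3–V4 interval is uninformative because the protocol bars rescue then. The interval definition is a proposal, since the protocol says only that the summary is by visit.

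If the sponsor prefers to keep the percent rule, record it in SAP 3.3 as a departure from the protocol.

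The cost is a few lines of SAP wording and four logit rows from eDiary data already collected.
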